Cover page

Official Title of the study:

Investigation of Real-time Diagnostic Ultrasound as a Means of Biofeedback Training in Transversus Abdominus Re-education of Patients With Non-specific Low Back Pain: Prospective Randomized Controlled Pilot Study

Date of the document: 4/5/2023

Document Type: Study Protocol with SAP

Background: It is believed that ultrasound-guided imaging of activation/contraction of the deep abdominal muscles (such as transversus abdominis) is useful for assisting deep muscle re-education, which is often dysfunctional in non-specific low back pain (NSLBP).

Objective: This pilot study's objective was to evaluate the use of real-time ultrasound (US) as a feedback device for transverse abdominis (TrA) activation/contraction during an exercise program in chronic NSLBP patients.

Methods: Chronic NSLBP patients are recruited and randomly assigned to an US-guided or control group. The same motor control-based exercise program is applied to both groups. All patients receive physiotherapy twice per week for 7 weeks. Outcome measures, test at baseline and post-intervention, include Numeric Pain Rating Scale (NPRS), TrA activation level (measured through a pressure biofeedback unit-based developed protocol), seven established motor control tests, Roland-Morris Disability Questionnaire (RMDQ) and Hospital Anxiety and Depression Scale (HADS).

Statistical Analysis Plan: Analysis of variance utilizing a two-way mixed analysis of variance (ANOVA) model for dependent measures of two factors (treatment group and time point of measurement) of which only one is repeated (time point of measurement) is performed to determine whether there were between- and within-group differences before and after treatment. Independent samples' t-test and paired samples' t-test are also used for differences between and within groups, respectively. An χ^2 test was also conducted for differences on the motor control tests and the TrA activation level procedure across the groups.

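### The only test named for TrA activation and the motor control tests is a chi-square across groups, which on post-treatment categories would leave the collected baseline and any ordering of levels unused

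*Combined protocol and SAP*

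**What the plan says.** All of this is in the combined protocol and SAP.

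- **Objective.** The pilot is to "evaluate the use of real-time ultrasound (US) as a feedback device for transverse abdominis (TrA) activation/contraction". TrA activation is therefore the listed outcome closest to the aim, although no outcome is called primary.
- **Methods.** "Outcome measures, test at baseline and post-intervention, include Numeric Pain Rating Scale (NPRS), TrA activation level", followed by "seven established motor control tests" and two questionnaires. A baseline result is thus collected for every listed outcome. How TrA level is graded and how the motor control tests are scored is not stated.
- **Statistical Analysis Plan.** A two-way mixed ANOVA with group and time as factors "is performed to determine whether there were between- and within-group differences before and after treatment". Then: "Independent samples' t-test and paired samples' t-test are also used for differences between and within groups, respectively". Neither sentence names an outcome.
- **Statistical Analysis Plan, last sentence.** A chi-square "test was also conducted for differences on the motor control tests and the TrA activation level procedure across the groups". This is the only sentence that ties a test to TrA activation or the motor control tests. It does not say which time point enters the table, what the categories are, or whether they are ordered.

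**The concern.** A Pearson chi-square of group by post-treatment category contains no baseline value and gives the same answer however the category columns are arranged. If TrA level is graded, two sources of information are lost: where each patient started, and the fact that one level is better than another.

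Randomisation keeps the comparison valid and unbiased, so neither bias nor a raised false-positive rate is at issue. What is at stake is precision on the outcome closest to the objective, in a pilot that has already collected the data needed to improve it.

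**Working it through.** **No figure to reproduce.** The documents give no sample size, power, alpha, effect size or scale. Every numerical input below is an assumption.

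**Step 1: does Pearson chi-square ignore order?** Take an invented table of four ordered levels with 20 per arm: 8, 6, 4, 2 against 3, 5, 5, 7. Column totals are 11, 11, 9, 9, so the expected counts per arm are 5.5, 5.5, 4.5, 4.5.

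- Pearson: 2 × (2.5²/5.5 + 0.5²/5.5 + 0.5²/4.5 + 2.5²/4.5) = 5.25 on 3 df, p = 0.154. Shuffling the columns leaves this unchanged.
- Trend test, (N − 1)r², with scores 0 to 3: arm means are 1.0 and 1.8, between-arm sum of squares 6.4, total 49.6. So r² = 6.4/49.6 = 0.129, and 39 × 0.129 = 5.03 on 1 df, p = 0.025. After a shuffle of the columns, p = 0.78.

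The Pearson test does not use order; the trend test does.

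**Step 2: what could that cost?** Monte Carlo, 20,000 replicates per cell, so the standard error is at most √(0.5 × 0.5/20,000) = 0.35 points.

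- Model: baseline X is standard normal; post-treatment Y = ρX + √(1 − ρ²)·e + d·G, with e standard normal and G the group indicator. Both are cut into 5, 3 or 2 levels, equally frequent at baseline.
- Main case: d = 0.8 SD, ρ = 0.5, two-sided alpha 0.05, 15/20/30 per arm.
- Adjusted test, graded outcome: rank ANCOVA (ranks of post level regressed on group and ranks of baseline level).
- Adjusted test, pass/fail outcome: Mantel-Haenszel by baseline result, [Σ(a − E(a))]²/ΣVar(a), where a is the number of passes in one arm within a baseline stratum, without continuity correction.

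Power (%) at 15/20/30 per arm, main case:

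| Test | Five levels | Three levels | Pass/fail |
|---|---|---|---|
| Chi-square on post level | 27/39/59 | 37/48/65 | 38/50/65 |
| Independent t-test on post codes | 51/64/81 | 47/58/76 | 38/49/65 |
| Mixed ANOVA group-by-time (equals t-test on change) | 44/56/74 | 37/48/65 | 26/36/50 |
| Chi-square on improved/not improved | 29/36/54 | 25/32/44 | 19/24/32 |
| Baseline-adjusted test | 58/72/88 | 52/64/82 | 39/52/69 |

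Gain of the adjusted test over the post-treatment chi-square, by subtraction:

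- Five levels: 31/33/29 points. Of this, 22 to 24 come from ordering and 7 to 9 from baseline.
- Three levels: 15/16/17 points.
- Pass/fail: 1/2/4 points. This becomes −1 to +1 at ρ = 0.3 and +6 to +10 at ρ = 0.7.
- With a continuity correction, Mantel-Haenszel power falls to 24/37/58%, below the uncorrected chi-square.

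**Step 3: sensitivity at ρ = 0.5** (chi-square → adjusted, %):

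| Change to main case | Five levels | Three levels | Pass/fail |
|---|---|---|---|
| Shift 0.5 SD | 12/17/25 → 28/36/51 | 18/21/31 → 25/32/45 | 18/23/32 → 19/25/35 |
| Baseline skewed to low levels | 29/40/61 → 59/72/89 | 37/48/67 → 51/65/82 | 39/48/65 → 39/49/68 |
| Both arms also improve 0.5 SD | 21/31/51 → 52/65/83 | 29/38/56 → 43/55/74 | 31/39/55 → 30/40/57 |

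**Step 4: is the gain an artefact of an inflated test?** With no effect, rejection is 3.5–5.5% for the chi-square, 4.6–5.3% for rank ANCOVA, 4.5–5.2% for uncorrected Mantel-Haenszel and 0.8–2.5% for the corrected version. The gain does not come from inflation; the corrected version is over-conservative at these sizes.

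A separate four-level simulation (15/25/40 per arm, 0.8 SD, ρ from 0.3 to 0.7) agrees in direction: ordering adds about 11 to 18 points, and ordering plus baseline about 13 to 36.

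**The case against.** The strongest reply is that the text establishes an ambiguity rather than an inefficient choice. The loss requires that the chi-square uses post-treatment categories, that the levels are ordered and number more than two, and that nothing else covers these outcomes. The ANOVA sentence excludes no outcome and follows a list of measures taken before and after treatment, and the chi-square is worded as an addition. On that reading baseline is already used. Equally, the choice of a chi-square suggests categorical measures, to which an ANOVA would be less natural. The text settles neither reading.

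This stands as a limit on the claim but does not remove it. By subtraction in the main-case table (a point either way for rounding), the adjusted test still gains 14/16/14, 15/16/17 and 13/16/19 points over the group-by-time test for five levels, three levels and pass/fail. Against the independent t-test it gains 7/8/7, 5/6/6 and 1/3/4. A chi-square on improved/not improved does use baseline, but has less power than the adjusted test in every cell.

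Two further points also stand. If the measures are pass/fail, the benefit is small and can be nil. And five levels is unfavourable to Pearson's test: at 15 or 20 per arm, more than 20% of expected counts fall below 5 in essentially every simulated trial, so an analyst might collapse levels, which moves the gain toward the three-level figures.

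**Conclusion.** The point holds, as a matter of efficiency and for consideration rather than as an error. The only test tied by name to TrA activation and the motor control tests would, if run on post-treatment categories, leave the baseline and any ordering unused.

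Under the assumed main case the gain from a baseline-adjusted test runs from about 30 points of power (five levels, mostly from ordering) through 15 to 17 (three levels) to 1 to 4 (pass/fail). For pass/fail it is about zero when baseline predicts little. Confidence is medium: the reading of the text is secure, but the scale, the chi-square's time point, the sample size and the reach of the other tests are all unstated.

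**What to change.** In the Statistical Analysis Plan:

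1. State the scale of TrA activation level and name one main between-group test for it: the post-treatment result compared between groups with adjustment for baseline.
2. If it is graded, use rank ANCOVA of post level on group and baseline level. Proportional-odds regression is an alternative where it is stable, but it may not be with few patients, so rank ANCOVA comes first.
3. If it is pass/fail, use Mantel-Haenszel stratified by baseline result, without continuity correction.
4. Do the same for the motor control tests, and say whether the seven are analysed singly or as a total.
5. State whether the mixed ANOVA and t-tests also cover these outcomes and, if so, that the baseline-adjusted test is the main one.

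The cost is SAP wording and slightly more analysis work; no extra data are needed. The past tense of the chi-square sentence suggests that the test may already have been run. If so, report the adjusted analysis beside it and label it as added later.

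### TrA activation level is assigned to a chi-square test with no ordered version named; if three or more ordered levels are recorded, an ordinary chi-square loses power against a consistent shift between arms

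*Combined protocol and SAP*

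**What the plan says.** The Objective is to evaluate real-time ultrasound as a "feedback device for transverse abdominis (TrA) activation/contraction during an exercise program in chronic NSLBP patients". No primary outcome is named, but among the outcomes listed under Methods the one closest to this aim is "TrA activation level (measured through a pressure biofeedback unit-based developed protocol". Methods gives no scale, number of categories or ordering for it.

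The Statistical Analysis Plan names one test for this outcome, a chi-square for "differences on the motor control tests and the TrA activation level procedure across the groups". It mentions no trend, rank or ordinal version, and does not say which time point, or whether change, enters the test. The mixed ANOVA and the t-tests are described without naming the outcomes they cover. The title calls the trial a "Prospective Randomized Controlled Pilot Study". Sample size, significance level, power and effect size are not stated.

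**The concern.** A Pearson chi-square on a table of two arms by k levels has k − 1 degrees of freedom and gives the same answer however the levels are arranged. If the levels run from poorer to better activation, a steady movement of one arm towards the better end earns no more credit than an irregular scatter of the same size. A test that uses the order puts its power on that movement, from the same table. If feedback training works, a consistent shift is the natural pattern to expect.

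At stake is the chance of seeing such a shift on the outcome nearest the objective, in a pilot likely to be small. The point does not depend on whether baseline is used: even a comparison of post-intervention levels alone would benefit from using the order.

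**Working it through.** The plan states no power or sample-size figure, so there is nothing to reproduce. The outcome, its planned test and the two-arm randomised design come from the document. Everything else below is assumed: 1:1 allocation, two-sided 5%, 2 to 5 levels, and a shift in one consistent direction.

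**Large-sample check.** Let λ be the noncentrality at which a 1-df ordered test has 80% power: P(χ²₁(λ) > 3.841) = 0.80 gives λ = 7.849. Give the unordered test the same λ on k − 1 degrees of freedom; its power is P(χ²ₖ₋₁(λ) > 95% critical value).

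| Levels | df | Chi-square power | Loss from 80% |
|---|---|---|---|
| 2 | 1 | 80.0% | 0 |
| 3 | 2 | 70.9% | 9.1 points |
| 4 | 3 | 64.5% | 15.5 points |
| 5 | 4 | 59.5% | 20.5 points |

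This assumes that the ordered test captures the whole difference, which is its most favourable large-sample case. For 3/4/5 levels the losses are 9.9/15.5/19.2 points at 50% reference power and 6.5/11.6/16.0 at 90%.

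**Simulation at pilot sizes.** A normal latent outcome is cut into equally frequent levels and one arm is shifted by 0.8 SD. Pearson chi-square is compared with the tie-corrected Wilcoxon test.

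| Per arm | Chi-square, 3/4/5 levels | Wilcoxon, 3/4/5 levels | Loss (points) |
|---|---|---|---|
| 15 | 38/33/29% | 47/50/50% | 9/17/21 |
| 20 | 48/44/40% | 59/62/64% | 11/18/24 |
| 30 | 67/65/61% | 77/80/82% | 10/15/21 |

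The loss therefore runs from 9 to 24 points. With two levels at 20 per arm, both tests have 48.5% power. With no true shift, both tests rejected in 3.7 to 5.6% of trials.

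**Smaller shifts, same model, 3 to 5 levels.** At 0.5 SD the loss is about 4–8 points at 10 per arm, 4–11 at 15, 6–14 at 20 and 9–18 at 30. A repeat run reached 19, hence about 4 to 19 overall. At 0.3 SD it is about 1–8 points across 10 to 30 per arm.

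**A different model.** With a proportional-odds shift set to give the Wilcoxon test about 80% power, the losses for 3 to 5 levels are about 12–30 points at 10 per arm, 10–24 at 20 and 9–21 at 50. At an odds ratio of 2 they are about 3–7 points at 10 per arm, 5–11 at 20 and 7–14 at 30.

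**Collapsing.** If five recorded levels were cut to two, power at 15/20/30 per arm would be about 39/49/70% against 50/64/82% for the ordered test on all five. The loss is 50 − 39 = 11, 64 − 49 = 15 and 82 − 70 = 12 points.

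**The case against.** The strongest reply is that no scale is given. The single chi-square sentence groups TrA activation with the motor control tests, which fits an achieved/not-achieved result just as well. In that case there is no order to ignore and nothing to change. This stands, and it makes the point conditional. A reader might infer from the word level that the measure is known to be graded and the test therefore known to be wrong; the document supports only the inference that it is apparently graded.

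Second, a linear trend test is itself a 1-df chi-square on the same table, and the plan does not say which chi-square it means. That is correct, but an unqualified chi-square across groups will ordinarily be run as Pearson's test, so the ordered version has to be named if it is intended.

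Third, TrA level is not expressly excluded from the ANOVA or the t-tests, so the chi-square may not be its only analysis. This stands too. Even so, the chi-square is the only test the plan ties to this outcome by name, and a possible second analysis would not make an unordered test a good match for ordered levels.

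Fourth, no hypothesis is written down. A reader might take the hypothesis to be directional, but the objective is only to evaluate the feedback method and the plan looks for differences between and within groups. The case for an ordered test rests on the pattern that successful training would be expected to produce, not on a stated hypothesis.

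Finally, nothing says that levels are collapsed to two. The collapsing figures show only what that would cost if it were done.

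**Conclusion.** The concern holds conditionally. The plan assigns an apparently graded outcome, the one nearest its objective, to a chi-square with no ordered version named. If three or more ordered levels are recorded and the difference is a consistent shift, an ordinary Pearson test gives up power in every setting examined. The size is illustrative: about 9 to 24 points for a 0.8 SD shift with 15 to 30 per arm, and about 4 to 19 points for a 0.5 SD shift with 10 to 30 per arm, with equally frequent levels and a two-sided 5% test. A truly pass/fail result carries no loss.

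A reader might take 9 to 24 points as this trial's actual loss. The documents do not support that: the range needs an effect size, arm size and number of levels that they do not give, and across the settings tried the loss runs from about 1 to 30 points. The direction is firm for three to five ordered levels; the amount is not.

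**What to change.** State in the plan what the TrA activation procedure records: the number of levels and their order. Keep the recorded level uncollapsed. If there are three or more ordered levels, replace the unordered chi-square for this outcome with one named between-arm test that uses order: a tie-corrected Wilcoxon-Mann-Whitney test, or a Cochran-Armitage (linear trend) test on the same arm-by-level table. Keep the chi-square for this outcome only if the procedure gives a pass/fail result.

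The cost is SAP wording alone; no further data, visits or patients are needed. The one small downside is that an ordered test is less sensitive to a non-monotone difference, such as one arm having more patients at both extremes.
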